## DRUG RECHALLENGE

Background: Following drug-induced liver injury, drug rechallenge is associated with a 13% mortality across all drugs in prospective studies [Andrade, 2009]. Clinical outcomes vary by drug, with nearly 50% fatality with halothane re-administered within one month of initial injury. However, some drugs seldom result in recurrent liver injury or fatality.

Risk factors for a fatal drug rechallenge outcome include:

- hypersensitivity [Andrade, 2009] with initial liver injury (e.g. fever, rash, eosinophilia)
- jaundice or bilirubin >2xULN with initial liver injury (direct bilirubin >35% of total)
- participant currently exhibits severe liver injury defined by: ALT $\geq$ 3xULN, bilirubin  $\geq$ 2xULN (direct bilirubin >35% of total), or INR $\geq$ 1.5
- prior serious adverse event or fatality has earlier been observed with drug rechallenge [Papay, 2009; Hunt, 2010]
- evidence of drug-related nonclinical liability (e.g. reactive metabolites; mitochondrial impairment [Hunt, 2010])

### VSLC Decision Process for Drug Rechallenge Approval or Disapproval

[figure not shown]
- Principal Investigator (PI) requests consideration of drug rechallenge for a participant receiving compelling benefit from a critical or life-saving drug, who exhibits liver chemistry elevation meeting participant stopping criteria in relation to DILI, with no alternative treatment
- By definition treatment naïve participants will only be considered for rechallenge if they were infected with a multi-resistant virus.
- Medical Monitor and Global Clinical Safety and Pharmacovigilance (GCSP) Physician review the participant's rechallenge risk factors (consultation with the Hepatotoxicity Panel is available) and complete checklist (Table 14).
- The local operating company (LOC) medical directors (ViiV and/or GSK where applicable) should be informed that study drug rechallenge is under consideration and of the final decision, whether or not to proceed.
- The Medical Monitor and GCSP Physician are accountable to review and agree on the following prior to preparing request for rechallenge documentation for presentation to VSLC:
  - Compelling benefit of the investigational product (IP) for this participant and no alternative therapy

- *must present source data defining the patient's current resistance profile with documented evidence of extensive drug resistance and previous drug history*
- Relative benefit-risk of drug rechallenge, with consideration of the following high risk factors:
  - Initial liver injury event included: fever, rash, eosinophilia, or bilirubin  $\geq 2xULN$  (or direct bilirubin  $>35\%$  of total, if available)
  - Participant currently exhibits severe liver injury defined by: ALT  $>3xULN$ , bilirubin  $>2xULN$  (direct bilirubin  $>35\%$  of total, if available), or INR $>1.5$
  - SAE or fatality has earlier been observed with IP rechallenge
  - IP is associated with known nonclinical hepatic liability/ injury
- Relevant physicians (listed below) must review and agree on action to be taken regarding request for drug rechallenge:
  - Safety Review Team Leader, Safety Development Leader, or Senior Safety Physician
  - Medicines Development Leader (MDL) and Project Physician Leader (PPL)
- Request is taken to full VSLC for final decision

**Table 14 Checklist for drug rechallenge for critical medicine (Following drug-induced liver injury, drug rechallenge is associated with 13% mortality across all drugs in prospective studies)**

	Yes	No
Compelling benefit of IP for this participant and no alternative therapy. Provide brief explanation:		
Relative benefit-risk favorable for drug rechallenge, after considering the following high risk factors:		
Initial liver injury event included:		
fever, rash, eosinophilia, or hypersensitivity		
bilirubin $\geq$ 2xULN (direct bilirubin >35% of total)		
Participant currently exhibits ALT >3xULN, bilirubin >2xULN (direct bilirubin >35% of total, if available), or INR>1.5		
SAE or fatality has earlier been observed with IP rechallenge If yes, please provide brief explanation:		
IP associated with known nonclinical hepatic liability/ injury		
Source data defining the patients current resistance profile		
Previous drug history		

**Figure 9 VSLC process for drug rechallenge approval or disapproval**

## DRUG RESTART

“Drug restart” can be approved by the VSLC for **transient, defined non-drug-induced** liver injury if no evidence of:

- immunoallergic injury /HLA association with injury
- alcoholic hepatitis

Study drug must be held while labs and evaluation are completed to assess diagnosis.

[figure not shown]
### VSLC Decision Process for Drug Restart Approval or Disapproval

- Principal Investigator (PI) requests consideration of drug re-initiation for a participant stable or improving on IP, who exhibits liver chemistry elevation meeting participant stopping criteria, which is transient, non-drug-related, and liver chemistries have improved to normal or are within 1.5x baseline and ALT < 5xULN.
- GSK Medical Monitor and GCSP Physician to review the participant’s diagnosis restart risk factors (Hepatotoxicity Panel consultation is available) and complete checklist (Table 15).
  - *must present source data defining the patient’s current resistance profile with documented evidence of extensive drug resistance and previous drug history.*
- The local operating company (LOC) medical director should be informed that study drug restart is under consideration and of the final decision, whether or not to proceed.
- Relevant physicians (listed below) must review and agree on action to be taken regarding request for drug restart:
- Safety Review Team Leader, Safety Development Leader, or Senior Safety Physician
- MDL and PPL
- Request is taken to VSLC for final decision

**Table 15 Checklist for Phase III drug restart after well-explained liver injury (e.g. biliary, pancreatic, hypotensive events, congestive heart failure (CHF), acute viral hepatitis), and improvement of liver chemistry to normal or  $\leq 1.5x$  baseline &  $ALT < 5xULN$**

	Yes	No
Is participant stable or improving on IP?		
Do not restart if the following risk factors at initial liver injury:		
fever, rash, eosinophilia, or hypersensitivity		
drug-induced liver injury		
alcoholic hepatitis (AST>ALT, typically <10xULN)		
IP has an HLA genetic marker associated with liver injury (e.g. lapatinib, abacavir, amoxicillin/clavulanate)		
Source data defining the patients current resistance profile		
Previous drug history		

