#### 5.5.1.3.1. *Drug Restart/Rechallenge. Following Liver Events that are Possibly Related to IP*

- Approval by the VSLC for drug restart or additional IM administration can be considered where:
- The participant is receiving compelling benefit, benefit of drug restart exceeds risk, and no effective alternative therapy is available. Ethics Committee or Institutional Review Board approval of drug restart/rechallenge must be obtained, as required.
- If the restart/rechallenge is approved by the VSLC in writing, the participant must be provided with a clear description of the possible benefits and risks of drug administration, including the possibility of recurrent, more severe liver injury or death.
- The participant must also provide signed informed consent specifically for the IP restart/rechallenge. Documentation of informed consent must be recorded in the study chart.
- Study drug must be administered at the dose specified by the VSLC.
- Participants approved by the VSLC for rechallenge of IP must return to the clinic twice a week for liver chemistry tests for a minimum of one month and thereafter for as long as clinically indicated and then laboratory monitoring may resume as per protocol. If protocol defined stopping criteria for liver chemistry elevations are met, study drug must be stopped.

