#### 5.5.1.3.2. *Drug Restart Following Transient Resolving Liver Events Not Related to IP*

Approval by the VSLC for drug restart or additional IM administration can be considered where:

- Liver chemistries have a clear underlying cause (e.g., biliary obstruction, hypotension and liver chemistries have improved to normal or are within 1.5 x baseline and ALT <3xULN). Ethics Committee or Institutional Review Board approval of drug restart/rechallenge must be obtained, as required.
- If restart/redosing of drug is approved by the VSLC in writing, the participant must be provided with a clear description of the possible benefits and risks of drug administration, including the possibility of recurrent, more severe liver injury or death.

- The participant must also provide signed informed consent specifically for the restart. Documentation of informed consent must be recorded in the study chart.
- Study drug must be administered at the dose specified by the VSLC.

Participants approved by the VSLC for restarting or re-dosing IP must return to the clinic once a week for liver chemistry tests for a minimum of one month and thereafter for as long as clinically indicated and then laboratory monitoring may resume as per protocol. If protocol defined stopping criteria for liver chemistry elevations are met, study drug must be stopped.

See Section 12.3, Appendix 3 for full guidance.

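### Appendix 3 asks for evidence of extensive drug resistance in a liver-event restart request, a rechallenge condition that almost no eligible participant could document

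*Protocol*

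**What the plan says.** The protocol separates two ways back to study drug after a liver stopping event. Rechallenge follows suspected drug-induced injury. Restart follows an event with an identified cause other than the drug.

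- **Rechallenge.** Section 5.5.1.3.1 allows it where "The participant is receiving compelling benefit, benefit of drug restart exceeds risk, and no effective alternative therapy is available". The Appendix 3 rechallenge process asks for "Compelling benefit of the investigational product (IP) for this participant and no alternative therapy" and places directly beneath it a requirement to present resistance data with evidence of extensive resistance. It adds that treatment-naive participants "will only be considered for rechallenge if they were infected with a multi-resistant virus".
- **Restart.** Section 5.5.1.3.2 turns on cause and recovery: "hypotension and liver chemistries have improved to normal or are within 1.5 x baseline and ALT <3xULN". It then refers the reader on: "See Section 12.3, Appendix 3 for full guidance". The Appendix 3 restart process requires the request to present "source data defining the patient’s current resistance profile", and the same line continues to the "current resistance profile with documented evidence of extensive drug resistance and previous drug history".
- **Force of the text.** Section 5.5.1.3 makes the guideline reproduced in Appendix 3 binding. Section 5.5.1.1 forbids a further injection until the VSLC approves.
- **ALT limit.** Section 5.5.1.3.2 sets <3xULN for restart, as does the restart text printed at the end of Section 7.4.4.6. The Appendix 3 restart process instead has "liver chemistries have improved to normal or are within 1.5x baseline and ALT < 5xULN", and Table 15 repeats the 5xULN figure.

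**The concern.** Extensive resistance has a clear purpose in rechallenge: it shows that the participant has no good alternative, which could justify re-exposure after drug injury. Restart does not depend on a lack of alternatives. It depends on the drug not being the cause and on the liver having recovered. In the restart process the line therefore asks for something unrelated to the decision, and something the trial's own entry criteria select against.

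At stake is the handling of a participant with, for example, resolved acute viral hepatitis, which Appendix 3 names as a restart case. Dosing is on hold and the request has a mandatory item that usually cannot be supplied. That invites delay, inconsistent handling or an avoidable discontinuation. Section 6.1 defines investigational product as the CAB and RPV formulations only, so before Week 52 any such loss falls on the CAB LA + RPV LA arm.

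**Working it through.** **1. The restart texts side by side.**

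| Restart text | What it turns on | Extensive resistance required? |
|---|---|---|
| Section 5.5.1.3.2 | Cause, recovery, ethics approval, consent, weekly tests | No |
| Section 7.4.4.6 (restart text) | Same | No |
| Appendix 3, definition of restart | Identified non-drug cause; no alcoholic hepatitis, hypersensitivity or HLA marker | No |
| Appendix 3, Drug Restart conditions | Transient non-drug injury; no immunoallergic injury or alcoholic hepatitis | No |
| Table 15, reasons not to restart | Hypersensitivity signs, drug injury, alcoholic hepatitis, HLA marker | No |
| Table 15, data lines | Resistance profile and previous drug history | No, profile only |
| Appendix 3, restart process sub-bullet | Profile, evidence of extensive resistance, drug history | **Yes** |

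Only the last row has the test, and its wording matches the rechallenge sub-bullet.

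**2. Who could meet it.** The synopsis schematic footnote requires no history of virologic failure. Inclusion 2 and Exclusion 4 rule out a switch made for treatment failure. Exclusion 26 rules out any known major INI or NNRTI mutation except K103N. The note to Exclusion 26 does not require prior genotyping, and Inclusion 4 requires HIV-1 RNA <50 c/mL at Screening. Section 7.8.1 ties on-study genotyping to confirmed virologic failure, and Section 5.5.5.3 discontinues those participants. NRTI and PI mutations are not expressly excluded, so the answer is almost nobody rather than nobody.

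**3. Size.** Section 9.2.1 gives 285 participants per arm. One avoidable discontinuation before the Week 48 window costs at most 1/285 = 0.0035, or 0.35 percentage points of long-acting-arm Snapshot response. The protocol gives no rate of non-drug liver events that meet stopping criteria. Assuming 1 to 5 such participants, for scale only, the range is 1/285 to 5/285 = 0.35 to 1.75 points, against a key secondary margin of -10 points. These are ceilings, because each participant would also have had to recover, consent, be approved and stay suppressed.

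**4. Primary endpoint.** Table 2, which reports LATTE-2 Snapshot outcomes, places discontinuation for an adverse event under no virologic data, not virologic failure. On that classification the effect on the primary failure rate is 0 points.

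**5. The ALT limits.** Exclusion 30 removes Screening ALT ≥3xULN. If baseline is also below 3xULN, recovery to within 1.5 times baseline means ALT below 1.5 × 3 = 4.5xULN. The 5xULN limit then never excludes anyone. The 3xULN limit does exclude, but only where baseline exceeds 3/1.5 = 2xULN. Example: baseline 2.8xULN with recovery to 4xULN gives a ratio of 4/2.8 = 1.43, which passes Appendix 3 and fails Section 5.5.1.3.2.

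**The case against.** The strongest reply is that the line does not block anything. It sits under the instruction to complete Table 15, and Table 15 carries it out as two yes/no lines that never mention extensive resistance. Lack of resistance is not among the listed reasons not to restart, and the VSLC takes the final decision. Section 5.5 requires withdrawal for liver toxicity only where no compelling alternate cause is found, and a restart case has such a cause by definition. All of this stands, and it limits the consequence. It does not make the mandatory wording suitable for restart.

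A reader might also infer that no resistance profile could exist at all. That goes too far. Section 7.8.2 allows resistance analysis on Baseline PBMC samples, and Section 7.2.2 speaks of Screening genotype results, although Section 7.2.1 and Exclusion 26 ask only for prior tests that are available. A profile may be obtainable. Evidence of extensive resistance is what eligible participants would lack.

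It can be argued that any obstacle to re-exposure is protective, since the injectables persist for more than a year in some people and the line between restart and rechallenge can be hard to draw. The liver safeguards, however, are the cause, recovery, hypersensitivity and HLA conditions, and none of them depends on viral resistance. Doubtful cases are already sent to rechallenge.

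That the line was copied over by mistake is inferred from the identical wording; the protocol does not say so.

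**Conclusion.** The point holds as a minor defect in a binding safety procedure. The restart process asks for evidence that serves only the rechallenge decision and that the entry criteria make almost unobtainable, so on a literal reading a complete package can rarely be assembled.

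Three stronger readings are not supported. First, the line is not shown to prohibit restart: it is a package item, and the committee may approve without it. Second, Section 5.5.1.3.2 is not contradicted on resistance: it is silent and defers to Appendix 3, so the line is an added condition. Third, the trial's conclusions are not threatened: the cost is at most 0.35 points of long-acting-arm Snapshot response per participant who stops before the Week 48 window, someone who stops after a suppressed in-window result costs nothing, and no material primary-endpoint effect or power loss follows.

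This rests on the text shown. Figure 10 and the separately maintained VSLC guideline are not available. It also assumes that Snapshot categories here follow those of Table 2. The ALT discrepancy is a separate inconsistency and does not raise the severity.

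**What to change.** In the Appendix 3 restart process, delete the words that require documented evidence of extensive drug resistance, so that the sub-bullet asks for the current resistance profile and previous drug history. Keep the two corresponding lines of Table 15 as they are. Keep the full phrase in the rechallenge process only. Check the separate VSLC guideline and make the same deletion there if the phrase appears. No new rule on missing resistance data is needed for this correction.

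Separately, change the restart ALT limit in the Appendix 3 process and in Table 15, including its title, from <5xULN to the stricter <3xULN of Sections 5.5.1.3.2 and 7.4.4.6.

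The cost is one deleted phrase and one changed limit within a single appendix, plus a check of the separate guideline by its owner. No assessment, sample size or analysis changes. The resistance edit leaves every cause and recovery condition in place, and the ALT edit tightens the appendix.

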**Figure 10 VSLC process for drug restart approval or disapproval**

## Medical monitor, GCSP Physician and PI actions for Restart or Rechallenge following VSLC decision

### Medical Monitor and GCSP Physician Actions

- Medical Monitor must notify PI of VSLC's rechallenge (or restart) decision and recommended dosing regimen in writing and Medical Monitor must record note in study files.
- The Safety Review Team must record rechallenge (or restart) outcomes and the GCSP Physician must send these to the VSLC (see template below).
- All severe reactions (rechallenge associated with bilirubin>2xULN or jaundice, or INR≥1.5), SAEs or fatalities which occur following a drug rechallenge (or restart) must be immediately reported to Line Management including, VSLC Chair, VP Global Medical Strategy and EU Qualified Person for Pharmacovigilance.

### PI Actions:

- The PI must obtain Ethics Committee or Institutional Review Board approval of drug rechallenge or restart, as required.
- If VSLC approves drug rechallenge or restart, the patient must sign a new informed consent containing a clear description of possible benefits and risks of drug administration including recurrent, more severe liver injury or possible death.
- ***Targeted drug rechallenge or drug restart consent form must be used.***
- The patient's informed consent must be recorded in the study chart, and the drug administered at agreed dose, as communicated by Medical Monitor.
- Liver chemistries must be followed ***twice weekly for 'rechallenge' cases*** and ***once weekly for 'restart' cases*** for a minimum of one month and thereafter for as long as clinically indicated following drug re-initiation. If participant exhibits protocol-defined liver chemistry elevations, IP should be discontinued as protocol specified.
- Medical Monitor and the Ethics Committee or Institutional Review Board must be informed of the patient's outcome following drug rechallenge or restart.

## Drug Rechallenge or Drug Restart Outcomes Table Template

To be completed/updated and provided to VSLC with each event recorded across studies and indications

### Drug Rechallenge/Restart Outcomes Table – Update with each event

Protocol#	Participant#	Rechallenge or Restart?	Safety outcome*	Drug benefit

#### Rechallenge/restart safety outcomes:

0 = no liver chemistry elevation

1 = recurrent liver chemistry elevation not meeting participant stopping criteria

2 = recurrent liver chemistry elevation meeting participant stopping criteria

3 = serious adverse event

4 = fatality

## 12.4. Appendix 4: CDC Classification for HIV-1 Infection (2014)

Note that the CD4+ T-lymphocyte count takes precedence over the CD4+ T-lymphocyte percentage in HIV infection stages 1, 2, and 3. The CD4+ T-lymphocyte should only be considered if the count is missing.

### HIV infection, stage 0

Indicates early HIV infection, inferred from a negative or indeterminate HIV test result within 180 days of a positive result. The criteria for stage 0 supersede and are independent of criteria used for other stages.

### HIV infection, stage 1

- Laboratory confirmation of HIV infection with no AIDS-defining condition, and
  - CD4+ T-lymphocyte count of  $\geq 500$  cells/ $\mu$ L, or
  - CD4+ T-lymphocyte percentage of total lymphocytes of  $\geq 26\%$ .

### HIV infection, stage 2

- Laboratory confirmation of HIV infection with no AIDS-defining condition, and
  - CD4+ T-lymphocyte count of 200 to 499 cells/ $\mu$ L, or
  - CD4+ T-lymphocyte percentage of total lymphocytes of 14% to 25%.

### HIV infection, stage 3 (AIDS)

- Laboratory confirmation of HIV infection, and
  - CD4+ T-lymphocyte count of  $< 200$  cells/ $\mu$ L, or
  - CD4+ T-lymphocyte percentage of total lymphocytes of  $< 14\%$ , or
  - Documentation of an AIDS-defining condition (see below).

Documentation of an AIDS-defining condition supersedes a CD4+ T-lymphocyte count of  $> 200$  cells/ $\mu$ L and a CD4+ T-lymphocyte percentage of total lymphocytes of  $> 14\%$ .

### HIV infection, stage unknown

- Laboratory confirmation of HIV infection, and
  - No information on CD4+ T-lymphocyte count or percentage, and
  - No information on presence of AIDS-defining conditions.

### Stage-3-defining opportunistic illnesses in HIV infection

- Candidiasis of bronchi, trachea, or lungs
- Candidiasis of oesophagus
- Cervical cancer, invasive
- Coccidioidomycosis, disseminated or extrapulmonary
- Cryptococcosis, extrapulmonary

- Cryptosporidiosis, chronic intestinal (>1 month's duration)
- Cytomegalovirus disease (other than liver, spleen, or nodes), onset at age >1 month
- Cytomegalovirus retinitis (with loss of vision)
- Encephalopathy, HIV-related
- Herpes simplex: chronic ulcers (>1 month's duration) or bronchitis, pneumonitis, or oesophagitis (onset at age >1 month)
- Histoplasmosis, disseminated or extrapulmonary
- Isosporiasis, chronic intestinal (>1 month's duration)
- Kaposi's sarcoma
- Lymphoma, Burkitt's (or equivalent term)
- Lymphoma, immunoblastic (or equivalent term)
- Lymphoma, primary, of brain
- Mycobacterium avium complex or Mycobacterium kansasii, disseminated or extrapulmonary
- Mycobacterium tuberculosis of any site, pulmonary, disseminated or extrapulmonary
- Mycobacterium, other species or unidentified species, disseminated or extrapulmonary
- Pneumocystis jirovecii pneumonia
- Pneumonia, recurrent
- Progressive multifocal leukoencephalopathy
- Salmonella septicaemia, recurrent
- Toxoplasmosis of brain, onset at age >1 month
- Wasting syndrome attributed to HIV.

